In order to predict these patient specific time-varying probabilities, the time scale is split into small intervals based on the visit schedules. In each interval the conditional probability of being switched given patient has not switched at any earlier interval is modelled using a logistic regression model with the following covariates–

- **Time independent (baseline) covariates:**

Age (in years), baseline LVEF, baseline eGFR (ml/min/1.73m²), history of prior MI (yes/ no), history of diabetes (yes/ no), Atrial Fibrillation associated with qualifying MI (yes/ no), baseline Killip class, use of PCI for qualifying MI (yes/ no), use of ACEI/ARB in last 24 hours prior to randomization (yes/ no), use of IV treatment for qualifying MI (yes/ no)

- **Time dependent covariates:**

Systolic BP (mmHg), Heart rate (bpm), eGFR (ml/min/1.73m²), *use of PCI or CABG (yes/ no), *use of ICD/CRT (yes / no)

(*procedures related to any post-randomization MI event)

Predicted probability of switching at a specific time for a patient will be obtained by multiplying individual conditional probabilities of switching in intervals prior to that time point. To minimize impact of extreme weights (e.g. patients not switched though having very high estimated probability to switch), the stabilized version of weights will be used which is defined as the ratio of predicted probabilities of not being switched by time t –

- from the logistic regression with only baseline covariates
- from the logistic regression with both baseline and post-baseline covariates

It is conceivable that the above logistic regression procedure of estimating weights may not converge due to reasons including (but not limited to) sparseness of switchers in the subpopulations implied by the selected covariates resulting into an infinite likelihood due to complete or quasi-complete separation or numerical difficulties in evaluating an overly complex likelihood function. Should such problems arise, the logistic regression model used to determine the IPC weights will be simplified by pooling pre-specified time intervals (thereby extending the time windows in which time-dependent covariates are assessed). If that still does not solve convergence problems, the model will be simplified by removing covariates.

All patients randomized to LCZ696 will be assigned a weight of 1 for all time intervals.

Estimation of treatment effect

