The estimand targeted in the original study protocol is defined in Table 2-3. In comparison, in a hypothetical world without COVID-19, the new intercurrent event due to COVID-19 is the onset of COVID-19 pandemic impact on study (see Table 2-4), which can be derived by a fixed global COVID-19 impact start date (01-Mar-

2020) or subject-specific impact start date based on information from the COVID CRF pages. A hypothetical strategy (see below methods i and ii) will be used for this new intercurrent event.

The analyses targeting this estimand will be performed with the following censoring methods:

- i. Endpoint data will be censored on 29-Feb-2020 if the patient has not experienced the endpoint by this time

This analysis will be performed using the primary analysis model as specified in [Section 2.5.2](#).

- ii. Endpoint data will be censored at the time of subject-specific COVID-19 impact start date, derived as the earliest date of the following for each patient based on the COVID-19 eCRF: (a1) study treatment discontinuation due to COVID-19; (a2) start of treatment interruption for > 3 months due to COVID-19; (b) first missed visit due to COVID-19; (c) first endpoint event impacted by COVID-19; (d) symptom onset of the first occurrence of a condition for which the patient felt the need to go to an outpatient clinic, urgent care, emergency department, or hospital but chose not to due to COVID-19.

This analysis will be performed using inverse probability of censoring weighted (IPCW) Cox proportional hazards model (Robins and Finkelstein 2000) as described in Section 2.6.5. IPCW is used to account for potential informative censoring using the subject-specific censoring method.

Table 2-3 Estimand in the original protocol :

Intercurrent event	Strategy
Permanent treatment discontinuation	Treatment policy strategy
Non-CV death	Hypothetical strategy

Primary scientific question of interest / Estimand:
 
What would be the relative risk reduction (HR) for Entresto vs Ramipril (regardless of treatment discontinuation) in patients with LV systolic dysfunction and/or pulmonary congestion following an AMI, in the composite primary endpoint, as measured by the time to first composite of CV death, HFH and outpatient HF, in the absence of death from non-CV related causes?
	

Table 2-4 Estimand in a world without the COVID-19 pandemic:

Intercurrent event	Strategy
Permanent treatment discontinuation	Treatment policy strategy

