2.6.5 Supportive analysis and sensitivity analysis

Supportive analysis

It is recognized that at the time of the first onset of symptomatic HF event some patients may discontinue randomized treatment and may be prescribed an alternative treatment for HF which could be locally available Entresto™ (sacubitril/valsartan, LCZ696). For the pre-specified secondary endpoints (1), (3) and (5) (numbering refers to Section 2.6.1), the analysis described in [Section 2.6.2](#) will estimate the treatment effect of LCZ696 vs ramipril including any effect of prescribed Entresto™ for ramipril patients who discontinued study drug and took Entresto™ as an alternative treatment. Hence, the following supportive analyses aim to estimate the pure treatment effect as though in a situation whereby Entresto™ was not an available treatment option for HFrEF. In this regard, as a sensitivity analysis, inverse probability of censoring weighted (IPCW) Cox proportional hazards model ([Robins and Finkelstein 2000](#)) will be performed on the secondary endpoints (1), (3) and (5).

Inverse probability of censoring weighted (IPCW) Cox proportional hazards model

In the IPCW analysis, the following censoring mechanism will be used for the event generating process for secondary endpoints:

- For patients randomized to LCZ696 and patients randomized to ramipril but did not take open label Entresto upon diagnosis of HFrEF event will be censored according to the mechanism described for the secondary endpoints.
- For patients randomized to ramipril who subsequently start taking open label Entresto, (defined as treatment switch), censoring will occur at the minimum of the last date the endpoint status was known, the time of death from non-CV causes, 28 days after study treatment discontinuation or start of open-label Entresto.

To adjust for the potential informative censoring, patients in the ramipril arm with event times censored due to treatment switch will be dynamically replaced in the patient risk-set by remaining uncensored patients in the ramipril arm with a matching prognostic profile by up-weighting such patients in the analysis set. At a specific time, patients in the ramipril arm who have not switched to taking open label Entresto will be assigned a weight inversely proportional to the probability of not switching till that time (i.e., patients who do not switch, but have covariates implying a high probability of switching, get a larger weight in the analysis).

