Estimating IPC weights

In order to predict these patient specific time-varying probabilities, the time scale is split into small intervals based on the visit schedules. In each interval the conditional probability of being switched given patient has not switched at any earlier interval is modelled using a logistic regression model with the following covariates–

- **Time independent (baseline) covariates:**

Age (in years), baseline LVEF, baseline eGFR (ml/min/1.73m²), history of prior MI (yes/no), history of diabetes (yes/ no), Atrial Fibrillation associated with qualifying MI (yes/no), baseline Killip class, use of PCI for qualifying MI (yes/ no), use of ACEI/ARB in last 24 hours prior to randomization (yes/ no), use of IV treatment for qualifying MI (yes/ no)

- **Time dependent covariates:**

Systolic BP (mmHg), Heart rate (bpm), eGFR (ml/min/1.73m²), *use of PCI or CABG (yes/ no), *use of ICD/CRT (yes / no)

*(*procedures related to any post-randomization MI event)*

Predicted probability of switching at a specific time for a patient will be obtained by multiplying individual conditional probabilities of switching in intervals prior to that time point. To minimize impact of extreme weights (e.g. patients not switched though having very high estimated probability to switch), the stabilized version of weights will be used which is defined as the ratio of predicted probabilities of not being switched by time t –

- from the logistic regression with only baseline covariates
- from the logistic regression with both baseline and post-baseline covariates

It is conceivable that the above logistic regression procedure of estimating weights may not converge due to reasons including (but not limited to) sparseness of switchers in the subpopulations implied by the selected covariates resulting into an infinite likelihood due to complete or quasi-complete separation or numerical difficulties in evaluating an overly complex likelihood function. Should such problems arise, the logistic regression model used to determine the IPC weights will be simplified by pooling pre-specified time intervals (thereby extending the time windows in which time-dependent covariates are assessed). If that still does not solve convergence problems, the model will be simplified by removing covariates.

All patients randomized to LCZ696 will be assigned a weight of 1 for all time intervals.

Estimation of treatment effect

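### SAP 2.6.5 builds the IPCW weights from a product of conditional switching probabilities, which cannot give the probability of not being switched that its own weight definition needs

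*SAP*

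**What the plan says.** SAP 2.6.5 plans an IPCW Cox model for secondary endpoints (1), (3) and (5). Ramipril patients who start open-label Entresto are censored, and the remaining ramipril patients are up-weighted to stand in for them. The section makes four statements about the weights:

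- **What is modelled.** In each visit-based interval, "the conditional probability of being switched given patient has not switched at any earlier interval is modelled" by logistic regression.
- **How intervals are combined.** The predicted probability of switching at a given time is "obtained by multiplying individual conditional probabilities of switching in intervals prior to that time point".
- **What the weight is.** A ramipril patient who has not switched is "assigned a weight inversely proportional to the probability of not switching till that time". The stabilised weight is "the ratio of predicted probabilities of not being switched by time t", with the baseline-covariate model in the numerator and the model with baseline and post-baseline covariates in the denominator.
- **Fallback.** If the logistic model does not converge, it is "simplified by pooling pre-specified time intervals" and then, if needed, by dropping covariates.

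The combining sentence is also in the SAP version written for the original protocol: "Predicted probability of switching at a specific time for a patient will be obtained by multiplying individual conditional probabilities of switching". The visible SAP amendment tables list other edits to 2.6.5 but no correction of this sentence. Protocol 9.5.1 leaves the implementation details to the SAP.

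SAP 2.5.4 reuses the method for a sensitivity analysis of the primary endpoint: "Endpoint data will be censored at the time of subject-specific COVID-19 impact start date", with IPCW as described in 2.6.5. Section 2.6.5 also states: "All patients randomized to LCZ696 will be assigned a weight of 1 for all time intervals".

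**The concern.** The combining sentence and the weight definition do not fit together. The definition needs the probability of not having switched by time t. The only computational rule given multiplies probabilities of switching, and nothing visible says how to get from one to the other. The rule's result shrinks as intervals are added, whereas the probability of having switched by a given time can only stay level or rise.

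These analyses are meant to show the treatment contrast as if open-label Entresto had not been available to ramipril patients. If the weights collapse to 1, what remains is plain censoring at switch, which is the potentially informative censoring that the weights were introduced to address. The output would still be labelled as an IPCW analysis.

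**Working it through.** The documents state no figure for this step, so there is none to reproduce. The check is algebra followed by an illustration.

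**Algebra.** Let p_k be the probability of switching in interval k given no earlier switch.

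- Not switched after K intervals: ∏(1 − p_k).
- Switched by then: 1 − ∏(1 − p_k).
- First switch in interval K: p_K × ∏(1 − p_j) over j < K.
- The SAP's rule: ∏ p_k. For K > 1 this matches neither switching probability, and 1 − ∏ p_k does not equal ∏(1 − p_k). They agree only at K = 1.

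**Constant-p illustration (assumed p = 0.05).** Cumulative switching after 1, 2, 3 and 9 intervals is 5.0%, 9.8%, 14.3% and 37.0%. The SAP's product is 5.0%, 0.25%, 0.0125% and about 0. A simulation of 400,000 patients with p = 0.05 and eight intervals gave 0.336 switched, against 0.337 from the correct formula and 3.9 × 10⁻¹¹ from the product.

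**Inputs for the weights.**

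- Intervals: protocol Table 6-1 visits on days 7, 14, 28, 61, 122, 243, 365, 486 and 608, so K = 9 at month 20. Planned mean follow-up is 19 months (SAP 1.1).
- Anchor: SAP Table 3-6, footnote 2, puts first HF hospitalization or outpatient HF at 10.3% (pooled) by 18 months. SAP 2.6.5 describes switching as arising at the first symptomatic HF event.
- Assumptions: switching mostly follows such an event, and p is constant across intervals. Average p is then 1 − (1 − 0.103)^(1/9) = 0.012.

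**Formulas.** With p_b from the baseline-covariate model and p_f from the full model:

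- Correct stabilised weight: [(1 − p_b)/(1 − p_f)]^K.
- Literal rule (one minus the product): (1 − p_b^K)/(1 − p_f^K).

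**Results with p_b = 0.012.**

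| Intervals K | Correct, p_f = 0.024 | Literal, p_f = 0.024 | Correct, p_f = 0.048 | Literal, p_f = 0.048 |
|---|---|---|---|---|
| 1 | 1.012 | 1.012 | 1.038 | 1.038 |
| 2 | 1.025 | 1.000 | 1.077 | 1.002 |
| 3 | 1.037 | 1.000 | 1.118 | 1.000 |
| 9 | 1.12 | 1.00 | 1.40 | 1.00 |

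For example, (0.988/0.952)^9 = 1.40, while (1 − 0.012^9)/(1 − 0.048^9) = 1.00.

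**How general the collapse is.** Under the literal rule the weight cannot exceed 1/(1 − p_f^K), whatever the baseline model gives. At p_f = 0.20 that ceiling is 1.042 at K = 2 and 1.008 at K = 3. At p_f = 0.50 it is 1.333 and 1.143, so the collapse is slower at large probabilities. The pooling fallback also slows it. With a single pooled interval the literal rule and the correct weight coincide.

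**The case against.** The strongest reply is that the SAP's intention is clear. Both statements of the weight refer to not switching, and the section says that non-switchers with a high probability of switching should count for more. Given a per-interval conditional model, the probability of not having switched by t has only one value. A careful programmer would use it. That stands: the sentence reads as a slip for multiplying the probabilities of not switching. It remains the only combining rule stated, in the document to which the protocol assigns these details.

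Three stronger readings are tempting, and the documents do not support them.

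- **Raw products in the ratio.** A reader might put the products straight into the stabilised ratio and conclude that weights for high-risk patients fall towards zero. The SAP excludes this: its ratio is of probabilities of not being switched, and its stated direction is the opposite.
- **Very large lost weights.** Assumed baseline/full probabilities of 0.02/0.10 or 0.05/0.20 give correct month-20 weights of 2.15 and 4.70. These are tail patients, at four to five times the baseline-model probability in every interval. At 0.20 per interval, 1 − 0.80^9 = 87% would have switched by month 20. Baseline probabilities of 0.10 to 0.30 would mean 27% to 66% switched by day 28. Nothing in the documents suggests such rates.
- **A wrong or biased result.** The text is a specification error. It does not show that the analysis was programmed this way, and no hazard-ratio bias can be derived from it.

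It is also fair that only supportive and sensitivity analyses are involved.

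**Conclusion.** The point holds as a specification error. The combining rule in SAP 2.6.5 is wrong for more than one interval and is incompatible with the weight definition beside it. That conclusion is algebraic and rests on no assumed rate.

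The size does rest on assumptions: switching mostly follows a first HF event, p is constant at about 0.012 over nine intervals of unequal length, and the patient's risk is two to four times average throughout. On that basis a month-20 weight of about 1.12 to 1.40 would become 1.00 under the literal rule, and the adjustment would be largely gone by the second or third interval.

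The scope is the supportive IPCW analyses of secondary endpoints (1), (3) and (5). The subject-specific COVID-19 analysis of the primary endpoint inherits the sentence by cross-reference, but no size is shown for it. The primary and main secondary analyses, alpha and the testing hierarchy are untouched. The correction should be made because it is cheap and the text is otherwise an unsafe programming specification.

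**What to change.** Replace the combining sentence in SAP 2.6.5 with: *The predicted probability of remaining unswitched by time t is the product, over the intervals before t, of one minus the conditional probability of switching in each interval.* Apply it to both the numerator model (baseline covariates) and the denominator model (baseline and post-baseline covariates). Keep the SAP's existing convention of using intervals before the time point. Check the weight code against this form before database lock.

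A separate point arises because SAP 2.5.4 sends the subject-specific COVID-19 analysis to 2.6.5. State in 2.5.4 that the same product form is used with COVID-19 impact in place of switch, and that weights are estimated in both arms. That censoring occurs in both arms, so fixing every LCZ696 weight at 1 does not carry over.

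The cost is one sentence in each section and a code check. No new data are needed, and the covariates and the Cox model do not change.

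### SAP 2.5.4 method ii handles COVID-19 censoring in both arms with a weighting recipe that adjusts ramipril only, and the recipe itself has a wrong product rule and a mismatched stabilising numerator

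*SAP*

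**What the plan says.** SAP 2.5.4, method ii, applies if the trial continues past the second interim analysis. Each patient's primary endpoint is censored at a COVID-19 impact date, "derived as the earliest date of the following for each patient based on the COVID-19 eCRF", with no restriction by arm. One trigger is "symptom onset of the first occurrence of a condition for which the patient felt the need to go to an outpatient clinic, urgent care" or similar, where the patient then stayed away because of COVID-19. The weighting is by cross-reference: the IPCW Cox model is used "as described in Section 2.6.5. IPCW is used to account for potential informative censoring using the subject-specific censoring method".

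SAP 2.6.5 deals with a different event, which it defines in one arm: "For patients randomized to ramipril who subsequently start taking open label Entresto, (defined as treatment switch), censoring will occur". Ramipril patients who have not switched "will be assigned a weight inversely proportional to the probability of not switching till that time". For the other arm the rule is "All patients randomized to LCZ696 will be assigned a weight of 1 for all time intervals".

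On computing the weights, 2.6.5 says: "Predicted probability of switching at a specific time for a patient will be obtained by multiplying individual conditional probabilities of switching in intervals prior" to the time point. The next sentence says "the stabilized version of weights will be used which is defined as the ratio of predicted probabilities of not being switched by time t". The numerator model has ten baseline covariates: age, LVEF, eGFR, prior MI, diabetes, atrial fibrillation, Killip class, PCI, recent ACEI/ARB use and IV treatment. The denominator model adds post-baseline covariates. The weighted Cox model is stratified by STEMI/NSTEMI and contains treatment, region and PCI.

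**The concern.** **(a) One-arm weighting.** Fixing LCZ696 weights at 1 is correct for the Entresto switch, because LCZ696 patients are not censored for it. COVID-19 impact censors both arms. If the Entresto-switch weights are carried over, COVID-19 censoring is not adjusted at all. If COVID-19 weights are fitted but the LCZ696 rule is kept, only ramipril is corrected. The stay-away trigger makes it plausible that censoring depends on current risk. Restoring the risk mix in one arm only then distorts the comparison.

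**(b) Product rule.** A product of switching probabilities shrinks as intervals accumulate, which a cumulative probability cannot do. It contradicts the section's own definition of the weight.

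**(c) Numerator.** Stabilising on baseline covariates is valid only if the outcome model conditions on them too. Nine of the ten are not in the Cox model, so any dependence of switching on those nine cancels out of the weight and remains uncorrected.

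At stake are this COVID-19 sensitivity analysis of the primary endpoint and the supportive IPCW analyses of secondary endpoints (1), (3) and (5).

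**Working it through.** The plan gives no figure for any IPCW analysis, so there is none to reproduce.

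**Inputs from the plan** (SAP 3.2, same in protocol 9.8.2)
- Pooled cumulative rates at 3/6/12/18 months: primary 7.2/8.6/11.0/13.0%; endpoint (3) 4.6/6.0/8.7/11.0%. Hazard constant after month 12.
- Accrual: 463 by month 10, 2,400 by month 24, then 250 a month to month 37 (2,400 + 13 × 250 = 5,650).
- Calendar: protocol Amendment 3 (01-May-2019) reports over 3,500 randomized. 2,400 + 250 × 4.4 = 3,500 falls at about month 28, so 1-Mar-2020 is set at month 38 and 31-Dec-2020 at month 48.
- Plausibility check: the model puts 24–25% of events after 1-Mar-2020; the SAP 5.4 code assumes 184/724 = 25%.

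**(a) Assumptions.** A two-state risk covariate, with 0 or 20% high-risk at baseline and 1–2% a month becoming high-risk. Event HR for high-risk 1.5–3. Monthly COVID-19 censoring 2–5% (low-risk) versus 4–25% (high-risk), the same in both arms, which censors 20–64% of those at risk on 1-Mar-2020. The weight model sees the true risk state and calendar month; the numerator conditions on baseline risk. The stress grid adds 4% a month becoming high-risk, event HR 5, and censoring of 10% versus 30–50%.

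**(a) Method.** Exact monthly expectations under a true HR of 1, solving the weighted Cox score equation for the HR.

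| Weighting | HR, moderate grid | HR, stress extreme |
|---|---|---|
| None | 1.000 | 1.000 |
| Both arms | 1.000 | 1.000 |
| Ramipril only, SAP-stabilised | 0.972–0.999 | 0.953 |

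Standard error of log HR = 2/√events: 2/√540 = 0.086 and 2/√724 = 0.074. Largest moderate shift: |ln 0.972| = 0.0284, and 0.0284/0.0861 = 0.33, 0.0284/0.0743 = 0.38 standard errors. Stress: |ln 0.953| = 0.0481, or 0.56 to 0.65 standard errors. If censoring depends on baseline risk only, the stabilised weights equal 1: the HR is 1.000 and nothing is adjusted.

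**(a) Separate simulation.** 1,000,000 patients per arm, 24 monthly intervals, the same covariate-dependent censoring mechanism in both arms from month 12, true censoring probabilities in the weights; Monte Carlo error about 0.003 on log HR.

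| Scenario | Target HR | Both arms, stabilised | Ramipril only, stabilised |
|---|---|---|---|
| True HR 0.81, about 40% censored, high-risk more | 0.813 | 0.813 | 0.790 |
| True HR 0.81, about 25% censored, high-risk more | 0.813 | 0.813 | 0.804 |
| True HR 0.81, low-risk censored more | 0.813 | 0.813 | 0.820 |
| True HR 1.0, about 40% censored, high-risk more | 0.996 | 0.997 | 0.970 |
| Non-informative censoring | 0.805 | 0.805 | 0.805 |

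**(b) Product rule.** With p_j the conditional probability of switching in interval j, P(not switched through k) = ∏(1 − p_j). For p = 0.02 over six intervals the written rule gives P(switch) = 0.02⁶ = 6.4 × 10⁻¹¹; the correct value is 1 − 0.98⁶ = 0.114. Stabilised example with baseline-only p = 0.02, full-model p = 0.10 and five intervals: correct weight 0.98⁵/0.90⁵ = 1.53. If one minus the written product is used (a step the SAP does not spell out), (1 − 0.02⁵)/(1 − 0.10⁵) = 1.00.

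**(c) Numerator.** Assumed: 20–30% high-risk, ramipril switching 0.05–0.2% versus 0.4–2% a month driven by baseline risk (2.5–13% switching overall), event HR 1.5–3, true HR 1. The SAP numerator gives HR 1.002–1.050; a numerator with interval only gives 1.000. In the simulation with censoring driven by a baseline covariate outside the Cox model, the ramipril hazard in months 12–24 stays at 8.90 per 1,000 a month with SAP stabilisation. The target is 9.67, and unstabilised weights give 9.68.

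**The case against.** The LCZ696 rule is right where it stands. Method ii states that its purpose is to deal with the subject-specific censoring, so a sensible programmer could model COVID-19 impact in both arms and drop the rule. On that view the text is under-specified rather than wrong. This reading is possible, but it discards a written rule and supplies a censoring model, covariates and LCZ696 weights that the SAP does not contain.

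Several points on size do stand:
- **Direction is conditional.** The shift reverses if low-risk patients are censored more and vanishes if censoring is non-informative. Site closures and travel restrictions need not track patient risk.
- **The figures in (a) assume that the weight model sees true risk.** The listed time-dependent covariates do not include HF symptoms. In a simpler unstaggered cohort with event HR 3 and monthly censoring of 5% versus 25%, the null HR was 0.943 with perfect observation, 0.991 with a proxy of 80% sensitivity and specificity, and 0.997 at 70%.
- **(a) and (b) do not add up.** If the product sentence is programmed literally and its complement taken, the weights collapse to about 1 (HR 0.811 against 0.812 unweighted). The one-arm bias appears once that sentence is corrected.
- **(b) is probably a drafting slip**, since the neighbouring sentences give the right definition.
- **(c) is partly a bias–variance choice.** SAP 2.6.5 describes switching at HF onset, which is post-baseline, so only the baseline-driven part of switching is affected.
- **Other COVID-19 analyses exist**, including fixed-date censoring, the Bayesian mixture prior and the time-varying Cox model.

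**Conclusion.** The concern holds. Following the text of method ii corrects COVID-19 censoring in ramipril only or not at all. The one-arm correction can be worse than no weighting: with equal informative censoring in both arms, the unweighted HR stayed at or within 0.001 of its target. The direction favours LCZ696 when higher-risk patients are censored more, in an analysis meant to test robustness. The likely size is small, below 0.4 standard errors in the moderate grid. It depends on assumed censoring rates, covariate effects and observation of risk, none of which the documents give. The product sentence is wrong as written and contradicts the section's own definition. The numerator mismatch is real for nine of ten covariates and works against LCZ696 if higher-risk ramipril patients switch more. The supportive and sensitivity analyses should be corrected; the confirmatory analysis is untouched.

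**What to change.** - **SAP 2.5.4, method ii:** state that a model for COVID-19-impact censoring is fitted and its weights applied in both arms, and that LCZ696 = 1 applies only to the Entresto-switch analysis. List the covariates, allowing for treatment arm and calendar time.
- **SAP 2.6.5, product sentence:** replace it with the statement that, with p_j the conditional probability of switching in interval j, the probability of remaining unswitched through interval k is the product over j ≤ k of (1 − p_j).
- **SAP 2.6.5, numerator:** restrict it to interval plus the covariates in the weighted Cox model, or add the numerator's baseline covariates to that model. The first option gives more variable weights; the second departs from the main-analysis model.

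The cost is SAP wording, one extra censoring model and slightly wider intervals (the widening was not computed).
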